9.5 Ipsilateral Femoral Shaft Fractures

For patients with ipsilateral femoral shaft fractures, a time-to-event analysis will be conducted to assess the time to radiographic fracture healing of the ipsilateral femoral shaft fracture (Tables 21-24).

Table 21: Secondary Procedures for Ipsilateral Femoral Shaft Fracture and Reasons

Outcome	Definition
Unplanned Secondary Procedures for Ipsilateral Femoral Shaft Fracture (study event)	Any unplanned surgery related to the treatment of the ipsilateral femoral shaft fracture within 12 months of initial surgery. Specific unplanned secondary procedures include: 
 • Wound closure • Soft tissue procedure • Bone graft • Nail removal • Exchange nailing – retrograde intramedullary nailing • Exchange nailing – antegrade intramedullary nailing • Exchange nailing – Other IF • Nail conversion to plating • Retaining the nail and augmentation with plates • Ilizarov external fixation • Other
Reasons for Secondary Procedures	
 • Wound healing problem • Compartment syndrome

	
 • Deep infection • Superficial infection • Shortening • Nonunion • Implant failure/breakage • Prolonged pain at the fracture site • Other
--	---

Table 22: Secondary Procedures for Ipsilateral Femoral Shaft Fracture, According to Surgical Treatment (No Significant Interaction Between Implant Type and Supplementation Present)

Secondary Procedure	Variable	Overall N=	Surgical Treatment X N=	Surgical Treatment Y N=	P-Value
Re-operation	Adjudicated Data				
Procedure for Nonunion Bone Graft Nail Removal Exchange nailing – IF Proximal femur osteotomy	Adjudicated Data				

Table 23: Secondary Procedures for Ipsilateral Femoral Shaft Fracture, According to Nutritional Supplementation (No Significant Interaction Between Implant Type and Supplementation Present)

Secondary Procedure	Variable	Overall N=	Nutritional Supplementation X N=	Nutritional Supplementation Y N=	P-Value
Re-operation	Adjudicated Data				
Procedure for Nonunion Bone Graft Nail Removal Exchange nailing – IF Proximal femur osteotomy	Adjudicated Data				

Table 24: Secondary Procedures for Ipsilateral Femoral Shaft Fracture (Significant Interaction Between Implant Type and Supplementation Present)

[figure not shown]
Secondary Procedures	Variable	Overall N=	Surgical Treatment X N=	Surgical Treatment Y N=	Nutritional Supplementation X N=	Nutritional Supplementation Y N=	Hazard Ratio (95% CI)				P- Value
							Surgery X + Supplement X vs. Surgery Y + Supplement X	Surgery X + Supplement Y vs. Surgery Y + Supplement Y	Surgery X + Supplement X vs. Surgery X + Supplement Y	Surgery Y + Supplement X vs. Surgery Y + Supplement Y	
Wound Closure Wound healing problem Compartment syndrome Deep infection Superficial infection Shortening Nonunion Implant failure/ breakage Prolonged pain at the fracture site Other	Adjudicated Data										
Soft Tissue Procedure Wound healing problem Compartment syndrome Deep infection Superficial infection Shortening Nonunion Implant failure/ breakage Prolonged pain at the fracture site Other	Adjudicated Data										
Bone Graft Wound healing problem	Adjudicated Data										

Compartment syndrome Deep infection Superficial infection Shortening Nonunion Implant failure/ breakage Prolonged pain at the fracture site Other											
Nail Removal Wound healing problem Compartment syndrome Deep infection Superficial infection Shortening Nonunion Implant failure/ breakage Prolonged pain at the fracture site Other	Adjudicated Data										
Exchange nailing – Retrograde Intramedullary Nailing Wound healing problem Compartment syndrome Deep infection Superficial infection Shortening Nonunion Implant failure/ breakage Prolonged pain at the fracture site Other	Adjudicated Data										

Exchange Nailing – Antegrade Intramedullary Nailing Wound healing problem Compartment syndrome Deep infection Superficial infection Shortening Nonunion Implant failure/ breakage Prolonged pain at the fracture site Other	Adjudicated Data															
Nail Conversion to Plating Wound healing problem Compartment syndrome Deep infection Superficial infection Shortening Nonunion Implant failure/ breakage Prolonged pain at the fracture site Other	Adjudicated Data															
Retaining the Nail and Augmentation with Plates Wound healing problem Compartment syndrome Deep infection Superficial infection Shortening	Adjudicated Data															

Nonunion Implant failure/ breakage Prolonged pain at the fracture site Other											
Ilizarov External Fixation Wound healing problem Compartment syndrome Deep infection Superficial infection Shortening Nonunion Implant failure/ breakage Prolonged pain at the fracture site Other	Adjudicated Data										
Other Wound healing problem Compartment syndrome Deep infection Superficial infection Shortening Nonunion Implant failure/ breakage Prolonged pain at the fracture site Other	Adjudicated Data										

Figure 19: Kaplan-Meier Curves for Secondary Procedures for Ipsilateral Femoral Shaft Fracture (Significant Interaction Between Implant Type and Supplementation Present)

9.6 Other Follow-Up Data

Characteristic	Variable	Surgical Treatment X N=	Surgical Treatment Y N=	Nutritional Supplementation X N=	Nutritional Supplementation Y N=	Total N=
Patient's Weightbearing Status at Follow-up Visit, n (%)	8.2 Q7					
6 Months						
Non-Weightbearing						
Protective Weightbearing or Using Assistive Device						
Full Weightbearing						
12 Months						
Non-Weightbearing						
Protective Weightbearing or Using Assistive Device						
Full Weightbearing						
Patient Receiving Physiotherapy or Rehabilitation at Follow-up Visit, n (%)	8.2 Q8					
6 Weeks						
3 Months						
6 Months						
9 Months						

Characteristic	Variable	Surgical Treatment X N=	Surgical Treatment Y N=	Nutritional Supplementation X N=	Nutritional Supplementation Y N=	Total N=
12 Months						
Patient Taking Medications at Follow-up Visit, n (%)	8.2 Q9					
6 Months NSAIDS Calcium Steroid Medications						
12 Months NSAIDS Calcium Steroid Medications						
Secondary Procedures Planned for Patient After 12 Month Follow-up Visit, n (%)	8.4 Q20					

9.7 Adverse Events and Safety Outcomes

An adverse event (AE) is defined as any symptom, sign, illness, or experience that develops or worsens in severity during the study. AEs and safety outcomes will be reported using descriptive statistics including proportions and means with SD (**Table 25**).

Table 25: General Summary of Adverse Events

Characteristic	Variable	Surgical Treatment X N=	Surgical Treatment Y N=	Nutritional Supplementation X N=	Nutritional Supplementation X N=
List of AE, n (%) <Insert most common AE> <Insert 2 nd most common AE> <Insert 3 rd most common AE>	11.1 Q2				
Serious Adverse Events, n (%)	11.2 Q8				
Time from baseline to AE, mean (SD)	11.1 Q1				
Re-Hospitalized for AE, n (%) Yes No N/A – AE occurred during initial hospitalization N/A – AE occurred while hospitalized for another problem	11.2 Q5				
Treatment, n (%) No Active Treatment Medication(s) Re-operation Other	11.2 Q4				

Related to Surgical Treatment Arm, n (%) Related Probably Related Possibly Related Not Related	11.2 Q6				
Related to Nutritional Supplementation, n (%) Related Probably Related Possibly Related Not Related	11.2 Q7				
Event Unexpected, n (%) Yes No	11.2 Q9				
Outcome, n (%) Not yet resolved Fatal Resolved with no impairment Resolved with mild impairment Resolved with moderate impairment Resolved with severe impairment	11.3 Q11				
Operative Adverse Event Yes	4.2 Q17				

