7.6 Adverse Event Reporting and Definitions

7.6.1 Adverse Event

An AE is any symptom, sign, illness, or experience that develops or worsens in severity during the course of this study. As FAITH-2 is not assessing patient safety, only AEs that are study outcomes (i.e. fracture-related) will be recorded as per sections 4.8.1 and 4.8.2.

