7.6.2 Serious Adverse Event

AEs are classified as serious or non-serious. A SAE is any AE that is any of the following:

- Fatal
- Life threatening
- Requires or prolongs hospital stay
- Results in persistent or significant disability or incapacity
- A congenital anomaly or birth defect
- An important medical event

All SAEs must be recorded and promptly submitted to the Methods Centre.

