7.8 Potential Risks to Participants

Surgeons worldwide are currently using both surgical techniques (cancellous screws and SHS). Both implants have been used for over five decades in the management of hip fractures. As with any surgical procedure of the lower extremity, potential risks include wound infection, deep vein thrombosis, neurovascular injury, and death. Given that all eligible patients require surgery for their acute fracture, there is no anticipated increased surgical risk for study participants. Similarly, the safety of vitamin D₃ supplementation is well established, and 4,000 IU per day is within the tolerable daily dose according to Health Canada.³⁶ Participants will be monitored for all SAEs and fracture-related AEs following treatment across the surgical and nutritional arms. The DSMC will review SAEs and fracture-related AEs at regular intervals.

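### SAP Table 25 shows adverse event types by arm only for the three most common events and gives serious events as one total, so serious deep vein thrombosis and neurovascular injury have no assured by-arm row

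*Combined protocol and SAP*

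**What the plan says.** SAP 9.7 states that "AEs and safety outcomes will be reported using descriptive statistics including proportions and means with SD". Its Table 25 names event types through three placeholders, beginning with "List of AE, n (%) <Insert most common AE>" and followed by the second and third most common, linked to CRF item 11.1 Q2. Serious events have one row, "Serious Adverse Events, n" with a percentage, not divided by type. The remaining rows give, by arm, time to event, re-hospitalization, treatment, relatedness to each intervention, unexpectedness, outcome ("Outcome, n (%) Not yet resolved Fatal Resolved with no impairment" and further categories) and a yes count for operative adverse events.

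On collection, protocol 7.6.1 says that "only AEs that are study outcomes (i.e. fracture-related) will be recorded as per sections 4.8.1 and 4.8.2". Serious events are treated differently in 7.6.2: "All SAEs must be recorded and promptly submitted to the Methods Centre". Protocol 7.8 says that "potential risks include wound infection, deep vein thrombosis, neurovascular injury, and death", and undertakes to monitor all SAEs and fracture-related AEs in both the surgical and the nutritional comparison.

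**The concern.** Choosing which event types to show by how often they occurred favours common events over rare serious ones. Non-serious events are recorded only when they are fracture-related study outcomes, so the three most common entries are likely to be complications that Tables 10, 11 and 19 already show. The three slots may then add little.

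The SAE record matters more. Under 7.6.1 and 7.6.2, a harm unrelated to the fracture is assured of entering the adverse event record only if it is serious. This applies particularly to the supplement comparison, where SAEs are the main route by which such a harm would be seen. If that record is reduced to one total, an excess of one serious event type in one arm can be absorbed into the total, and no planned table would separate it out.

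**Working it through.** The point concerns which rows exist, and there is no plan figure to reproduce. The check sets the risks named in protocol 7.8 against the collection rules (protocol 4.8.1, 4.8.2, 7.6.1 and 7.6.2) and against the SAP displays that could show a harm by arm (Tables 10 to 12, 19 and 21 to 25).

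| Risk named in protocol 7.8 | Assured of being recorded? | By-arm row in the SAP |
|---|---|---|
| Wound infection | Yes; infection and wound healing problems are secondary outcomes in 4.8.2 | Table 19: wound healing problems; superficial, deep and organ-space infection |
| Death | Yes; a fatal event is an SAE | Table 25, outcome row, fatal category |
| Deep vein thrombosis | Only if it meets an SAE criterion | None by name |
| Neurovascular injury | Only if it meets an SAE criterion; an intra-operative case may also be captured by CRF 4.2 Q17 | None by name; the operative event row does not give the type |

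Two of the four named risks therefore have an assured by-arm display and two do not. For those two, type is visible only through the top-three rows. Every other row of Table 25 describes a property of events (timing, treatment, relatedness, expectedness, outcome) and not their kind. Tables 10 to 12 classify re-operations by reason, and Tables 21 to 24 do so for the femoral shaft; neither set lists SAEs.

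How likely is either event to reach the top three? The documents give no rate, so only an assumed range can be shown, using expected events per arm = n × rate. The two values of n are 404 (half of the planned 808) and 43 (the surgical group size printed in the SAP Table 2 shell).

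| Assumed rate | n = 404 | n = 43 |
|---|---|---|
| 1% | 404 × 0.01 = 4.04 | 43 × 0.01 = 0.43 |
| 2% | 404 × 0.02 = 8.08 | 43 × 0.02 = 0.86 |
| 5% | 404 × 0.05 = 20.2 | 43 × 0.05 = 2.15 |

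For comparison, protocol 5.1 plans on a 25% control rate for the primary composite, or 404 × 0.25 = 101 participants in a control arm and 43 × 0.25 = 10.75 at the smaller size. Those are spread over four components, so the comparison is loose. It does suggest that an event at 1% or 2% could easily fall outside the top three; at 5% the ranking is less clear.

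**The case against.** The strongest reply has four parts.

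- **Table 25 is not limited to the top three and a total.** It also gives relatedness to each intervention, unexpectedness, fatal outcome and operative events by arm, and Table 19 lists specific complications. This stands. A reader might infer that the SAP shows none of the harms the protocol names, and that is not so. None of these rows, however, gives the type of a serious event.
- **The gap is not an exclusion.** The three rows are placeholders in a table titled as a general summary, either event could rank in the top three, and SAP 1.0 says that the plan reviews all data collected and will follow CONSORT 2010. A reader might infer that these events will never be compared by arm; the documents support only that the comparison is not assured. SAP 1.0 also leaves the choice of published data points to the Writing Committee, so the general statement does not prespecify a table. The DSMC's review of SAEs is monitoring during the trial, not final reporting.
- **The two events are not fully collected.** Protocol 7.6.1 says that the trial is not assessing patient safety, and neither event is a study outcome. Non-serious cases are not assured of recording, so a row meant to cover all cases would be incomplete. This stands and limits the remedy to serious cases. Section 7.8 also presents them as general risks of lower-limb surgery, not as safety endpoints.
- **No masking effect can be quantified.** The documents give no rate for these events and no expected SAE total, so a worked example of a hidden imbalance would rest wholly on invented counts. This stands, and none is offered.

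**Conclusion.** The point holds in a limited form. Followed as written, the SAP contains no by-arm table of SAEs by type, and two of the four risks named in protocol 7.8 are displayed by arm only if they rank among the three most common adverse events. That conclusion comes from reading the table shells and needs no assumption. The view that the two events may well miss the top three rests on assumed rates of 1% to 2% and on the expectation, plausible but not shown in the documents, that fracture-related outcomes fill those places. The primary analysis and the sample size are unaffected. This is a cheap improvement to a descriptive safety table.

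Separately, both supplementation columns of Table 25 carry the label X. Other SAP tables use X and Y, so this is a clerical slip with no bearing on the argument.

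**What to change.** Add to SAP 9.7 a table of all SAEs by type, by surgical group and by supplementation group, counting participants with at least one event of each type. Include fixed rows for serious deep vein thrombosis, serious neurovascular injury and death, so that zero counts are also reported. Add a footnote that non-serious cases of the first two are not systematically collected under protocol 7.6.1. No further infection row is needed, because Table 19 already covers it. Change the last column header of Table 25 to Nutritional Supplementation Y.

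The cost is an edit to the table shells and a longer safety section. The table draws on SAE records that 7.6.2 already requires and on the event item (CRF 11.1 Q2) that Table 25 already cites, so no new data collection is needed.

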4.6 Nutritional Supplementation

4.6.1 Administration of Nutritional Supplementation

Nutritional supplementation will be administered upon hospital discharge or within two weeks of the participant's femoral neck surgery, whichever comes first. Ideally, participants should be administered the nutritional supplementation as soon as possible following their surgery. Each participant will be provided with a six-month supply of vitamin D₃ supplementation or placebo.

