8.3 Central Adjudication Committee

The CAC will be comprised of four orthopaedic surgeons with prior adjudication experience and they will independently adjudicate the following:

- Situations where eligibility is in doubt
- Radiographic characteristics and quality of the surgery
- Patient important outcomes that define the primary outcome (re-operation, femoral head osteonecrosis, severe femoral neck malunion, or nonunion)
- Fracture healing complications
- Radiographic fracture healing

All clinical sites will submit X-Rays and any additional imaging studies (such as a hip MRI or other advanced imaging studies) to be included in the adjudication process (**Figure 7**). Clinical notes may also be requested. Any disagreements between the CAC members will be resolved during regular conference calls. If consensus cannot initially be reached, additional information will be requested from the clinical site to clarify areas of uncertainty.

Table 1: Schedule of Events

Assessment	Screening	Enrollment (Baseline)	Surgery	Post-operative	Week 6	Month 3	Month 6	Month 9	Month 12
Informed Consent	X								
Medical History	X								
AP & Lateral X-Rays of Proximal Femur	X			X	X	X	X	X	X
Physical Exam/Injury Assessment	X								
Screening Form	X								
Randomization Form		X							
Pre-Operative Form		X							
Surgery (SHS or Cancellous Screws)			X						
Surgical Forms			X						
Hospital Discharge Form				X					
Vitamin D or Placebo Supplementation**				X	X	X	X		
Follow-up Visit Forms				X	X	X	X	X	X
Assessment for Re-Operations				X	X	X	X	X	X
Assessment of Fracture Healing Complications					X	X	X	X	X
Assessment of Fracture Healing					X	X	X	X	X
Hip Outcome Score (HOS)				X*	X	X	X	X	X
Short Form-12 (SF-12)				X*	X	X	X	X	X
Assessment of Fracture Healing of the Ipsilateral Femoral Shaft Fracture***					X	X	X	X	X
Assessment for Fracture-Related Adverse Events			X	X	X	X	X	X	X
Assessment for Serious Adverse Events			X	X	X	X	X	X	X
Assessment for Planned Re-operations									X

*Asks about participant’s function prior to their hip fracture.

** Nutritional supplementation will be administered upon hospital discharge or within two weeks of the participant’s surgery, whichever comes first. Ideally, participants should be administered the nutritional supplementation as soon as possible following their surgery to repair their femoral neck fracture.

***For participant’s with an ipsilateral femoral shaft fracture.

Table 2: Sample Size Estimates

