5.0 INJURY AND FRACTURE CHARACTERISTICS

Injury details and fracture characteristics will be summarized in **Table 3**. Pre-operative and post-operative care details (**Table 4**) will be presented for each surgical treatment and nutritional supplementation group. Means and SDs will be used for continuous data, and categorical data will be presented as frequencies and proportions.

Table 3: Fracture Characteristics

Characteristic	Variable	Surgical Treatment X N=	Surgical Treatment Y N=	Nutritional Supplementation X N=	Nutritional Supplementation Y N=	Total N=
Level of the Fracture Line, n (%) Subcapital Midcervical Basal Unable to assess	Adjudicated Data					
Garden Classification, n (%) Garden I (undisplaced) Garden II (undisplaced) Garden III (displaced) Garden IV (displaced) Unable to assess	Adjudicated Data					
Pauwels' Classification, n (%) Type I Type II Type III Unable to assess	Adjudicated Data					
Mechanism of Injury, n (%) Motor Vehicle Accident (Driver/Passenger) Motor Vehicle Accident (Pedestrian) Motorcycle Accident Recreational Vehicle (4 Wheeler, Snowmobile, ATV, etc) Bicycle Accident Fall from Height (>1m) Fall from Height (≤1m) Fall from Standing Direct Trauma (Blunt) Direct Trauma (Penetrating)	3.3 Q15					
Additional Fractures, n (%) Upper extremity Lower extremity Spine and sacrum Pelvis	3.4 Q20					
Additional Injuries, n (%) Chest Injury Abdominal Injury Head/Neck Injury Soft Tissue Injuries to Extremities	3.4 Q24					

Characteristic	Variable	Surgical Treatment X N=	Surgical Treatment Y N=	Nutritional Supplementation X N=	Nutritional Supplementation Y N=	Total N=
Ipsilateral Femoral Shaft Fracture, n (%)	3.5 Q23					

Table 4: Summary of Pre-Operative and Post-Operative Care Details

Characteristic	Variable	Surgical Treatment X N=	Surgical Treatment Y N=	Nutritional Supplementation X N=	Nutritional Supplementation Y N=	Total N=
Pre-operative Antibiotic Prophylaxis, n (%)	3.5 Q26					
Discharge Location, n (%) Home Rehabilitation Facility Other Hospital Medical Respite	7.1 Q2					
Provided with Nutritional Supplement, n (%)	7.1 Q3					
Received Nutritional Supplement Within Two Weeks of Femoral Neck Surgery, n (%)	7.1 Q5					
Nutritional Instructions and Importance of Complying with Nutritional Supplementation Discussed with Participant, n (%)	7.1 Q6					

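### SAP Table 25 tabulates adverse events by supplement group from surgery onward with no split at first dose, so pre-dose events blur the vitamin D versus placebo safety comparison

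*Combined protocol and SAP*

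**What the plan says.** **Start of the supplement.** Protocol 4.6.1 has it "administered upon hospital discharge or within two weeks of the" participant's surgery, taking whichever comes earlier, and adds: "Ideally, participants should be administered the nutritional supplementation as soon as possible following their surgery". In protocol Table 1 (Schedule of Events) supplementation is first marked in the post-operative column. Dosing lasts six months and follow-up twelve.

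**Start of event collection.** In the same schedule, the row "Assessment for Serious Adverse Events" and the row for fracture-related AEs are first marked one column earlier, at surgery. Protocol 7.6.1 limits non-serious AEs to fracture-related ones; 7.6.2 requires all SAEs to be recorded.

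**How events are tabulated.** SAP 9.7 defines an AE as something that arises or worsens during the study, and plans descriptive statistics only. Table 25 has two implant columns and two supplement columns, and every row runs across all four. The rows include SAEs, "Time from baseline to AE, mean (SD"), a re-hospitalisation item with the level "N/A – AE occurred during initial hospitalization", an operative-AE item taken from the surgical form (4.2 Q17), and "Related to Nutritional Supplementation, n" (%).

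**What is not there.** Neither document defines a first-dose window, a treatment-emergent rule or a separate safety population. SAP 8.0 applies intention to treat to outcome analyses. SAP Table 4 has the item "Provided with Nutritional Supplement, n" (%) and a yes/no item on receipt within two weeks (7.1 Q3 and Q5), but no first-dose date.

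**The concern.** An event with onset before the first dose cannot have been caused by the supplement. Table 25 nevertheless counts such events in the vitamin D and placebo columns alongside later ones, and times them from baseline. The operative row is pre-dose by construction, because the supplement always follows the operation.

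What is at stake is sensitivity. Events that the supplement cannot influence raise the percentage in both groups by a similar amount. A true excess after dosing starts then stands out less, both as a ratio of percentages and against chance variation. Table 25 is the only SAP table that shows SAEs by supplement group, so a reader who wants that comparison has nowhere else to look. The same table also merges the six months of dosing with the six months that follow.

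**Working it through.** **1. Order of events.**

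| Item | First marked or defined | Source |
|---|---|---|
| AE and SAE assessment | Surgery | Protocol Table 1 |
| Supplement | Post-operative; discharge or by two weeks, whichever is earlier | Protocol Table 1, 4.6.1 |
| Time origin for AEs | Baseline | SAP Table 25 |
| Split at first dose | None | SAP 9.7, whole of both documents |

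There is thus a pre-dose interval, up to 14 days after surgery by protocol, in which events are collected and then shown under the supplement columns.

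**2. No plan figure to reproduce.** Table 25 is an empty shell and neither document states an AE or SAE rate. The following is an illustration under assumed rates, not an estimate for this trial.

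**3. Formula.** Let *b* be the pre-dose risk, equal in both arms because of randomisation. Let *p0* and *p1* be the post-dose risks on placebo and vitamin D, assumed independent of pre-dose events. The proportion with any event is

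*q* = 1 − (1 − *b*)(1 − *p*).

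The difference is then (1 − *b*)(*p1* − *p0*), and the ratio *q1*/*q0* moves towards 1 as *b* rises.

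**4. Numbers, assuming *p0* = 10% and *p1* = 20%.** With equal arms, the standard error of the difference, relative to *b* = 0, is √{[*q0*(1 − *q0*) + *q1*(1 − *q1*)] / 0.25}, since 0.10 × 0.90 + 0.20 × 0.80 = 0.25. This factor does not depend on the sample size.

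| *b* | *q0* | *q1* | Ratio | Difference (points) | SE factor |
|---|---|---|---|---|---|
| 0 | 10.0% | 20.0% | 2.00 | 10.0 | 1.00 |
| 5% | 14.5% | 24.0% | 1.66 | 9.5 | 1.11 |
| 10% | 19.0% | 28.0% | 1.47 | 9.0 | 1.19 |
| 20% | 28.0% | 36.0% | 1.29 | 8.0 | 1.31 |
| 30% | 37.0% | 44.0% | 1.19 | 7.0 | 1.38 |

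Worked line for *b* = 30%: *q0* = 1 − 0.70 × 0.90 = 0.37; *q1* = 1 − 0.70 × 0.80 = 0.44; 0.44/0.37 = 1.19; √[(0.2331 + 0.2464)/0.25] = 1.38.

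With a rarer event, 5% v 10%, the ratio of 2.00 becomes 1.49, 1.31, 1.17 and 1.10 at the same four values of *b*.

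**5. Event counts behave differently.** If events rather than patients are counted, the ratio is (*b* + *p1*)/(*b* + *p0*). For *b* = 10% that is 0.30/0.20 = 1.50. The difference stays at *p1* − *p0* = 0.10 per patient whatever *b* is; only its noise grows.

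**The case against.** The best defence is that Table 25 is a descriptive shell that reports everyone as randomised, which fits the intention-to-treat stance and the pragmatic framing of the supplement arm in protocol 4.6.4. It contains no ratio, interval or p-value. It also has a relatedness row for the supplement, a level for the initial admission and a separately labelled operative row, so a reader can pick out some of the early events. The pre-dose interval is at most two weeks of a twelve-month follow-up.

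Most of this stands, and it limits the point. It does not remove it. Relatedness is a judgement by blinded staff, not a split in time. The early-event rows are not cross-classified with SAEs or with type of event, so they cannot be subtracted from the rows that matter.

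A reader might go further than the documents allow in four ways:

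- *That events in the first admission are all pre-dose.* They are not. The earlier-of-two rule, the wish to dose as soon as possible, and stays beyond two weeks (patients with multiple traumas are eligible) all place some in-hospital events after first dose. Only operative events are pre-dose by definition, and the documents do not show whether these also enter the AE list or SAE count, which come from a different form.
- *That the table is biased towards one arm.* Randomisation balances pre-dose events on average.
- *That the DSMC will be misled.* The SAP covers the primary manuscript. Nothing says that the committee works from Table 25 or lacks onset dates.
- *That this is the only supplement safety comparison.* SAP Table 11 (re-operations) and Table 19 (infection, wound and implant complications) also compare harms by supplement.

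**Conclusion.** The point holds as a reporting weakness of minor weight. Operative events, and an unknown share of initial-admission events, fall before the first dose and are shown under the supplement columns without any time split. The effect is attenuation of patient-level percentages and of any ratio formed from them, plus added noise; differences in event counts are not attenuated. An event type that cannot occur before dosing is not diluted in its own row.

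The size cannot be fixed from the documents. The range of 1.66 to 1.19 for a true ratio of 2.00 rests on three assumptions: post-dose risks of 10% v 20%, an equal pre-dose risk of 5% to 30% in both arms, and independence of pre-dose and post-dose events. The primary analysis, the sample size and the implant comparison are untouched.

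**What to change.** Keep Table 25 for all randomised participants. In SAP 9.7, before unblinding:

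1. Add, for the supplement columns, AEs and SAEs split by onset before versus on or after first dose. Show the six-month dosing period separately from later follow-up, and measure time to event from first dose in the post-dose rows.
2. State the denominator for the post-dose rows and how participants who never received the supplement are shown. They stay in the all-randomised table in any case.
3. Show the operative-AE row under the implant columns only, or label it as pre-dose.
4. Confirm that the case report forms capture a first-dose date. The SAP tables show only whether the supplement was provided and whether it was received within two weeks (7.1 Q3 and Q5). If there is no date, add the field.

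There is no need to replace the all-randomised table with one restricted to dosed participants; an added split is enough.

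The cost is a few sentences, one extra table that draws on AE timing data already listed (11.1 Q1), and possibly one date field. The downside is fewer events in the post-dose rows, so wider uncertainty around each percentage. In the same edit, the two supplement column headings in Table 25, which both read X, should be corrected; that is a separate slip.
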